
Purpose/Objectives: Primary Aims
 
1: Evaluate the safety of high-dose spironolactone in combination of Patiromer in acute decompensated heart failure patients.
 
2: Evaluate the efficacy of high-dose spironolactone in combination of Patiromer in causing volume loss and symptom relief in patients with ADHF treated with high-dose spironolactone.
 
Secondary Aims
 
1: Evaluate the effect of high-dose spironolactone on urinary sodium excretion and renal function.
 
Research Design/Plan: We propose a prospective exploratory single-arm, open-label pilot study to assess the safety and efficacy of high dose spironolactone in combination with Patiromer in patients hospitalized with decompensation of chronic heart failure who shows sign of resistance of loop diuretics. Patients admitted with decompensated heart failure will be identified from the inpatient cardiology and internal medicine services.
 
Methods: Study Protocol
 
Pre-screening: Patients meeting the inclusion and exclusion criteria will be approached to participate in the study. Informed consent will be taken at this time. These patients will receive intravenous loop diuretic per the discretion of treating physician and will be closely followed for weight loss and symptoms relief.
 
Screening: The patients who don't respond as measured by symptoms relief or <0.5 kg weight loss/day
 
a) Despite furosemide \geq 160 mg IV total daily dose or equivalent dose of torsemide or bumetanide. (1 mg bumetanide = 10 mg torsemide = 20 mg furosemide). ORb) After 48 hours of admission irrespective of diuretic dose. 
will be considered for the study intervention. Patients who have not participated in the pre-screening phase and do not respond adequately to furosemide >160 mg iv daily dose will directly be enrolled into active intervention part of the study.
 
Intervention (High-Dose Spironolactone + Patiromer): Patients will be initiated on spironolactone 100 mg orally once daily along with patiromer 8.4 gm orally (if serum K >4.3 meq/L). The dose of loop diuretic will stay same during rest of the study period. On day 2, the dose of spironolactone will be titrated to 200 mg orally once a day depending on the diuretic response and lab results. Serum potassium and magnesium will be monitored twice a day. An EKG will be performed any time electrolytes are out of range. The dose of patiromer will be increased to 16.8 gm in patients with potassium levels exceeding 5.5 meq/L; or it will be held for serum K <4.3 mEq/L. Treatment will continue till patients achieve euvoolemia or get discharged. Euvoolemia is defined as resolution of symptoms and signs of volume overload.
 
Treatment Failures: Patients will be considered high dose spironolactone failure if they do not achieve a net negative body weight after a minimum of 5 days. High-dose spironolactone may be stopped anytime per the discretion of the treating physician. The patients that do not respond to high-dose spironolactone are considered treatment failures and will be included in the primary endpoint analysis.
 
Concomitant Medications/diet: Patient taking concomitant heart failure medications such as ACEi, ARB and/or beta-blockers are to be continued throughout the study as tolerated. If these medications have not been administered at the time of randomization, timing and sequence of the starting ACEi, ARB or beta-blockers will be left to the discretion of the treating physician. All the patients will be prescribed low Na (<1.5gm/day) and low potassium (50-75 mEq/day) diet.
 
Clinical Relevance: Insert response here
	

Item 3 Background 
Describe past experimental and/or clinical findings leading to the formulation of your study.
 
For research involving unapproved drugs, describe animal and human studies.
 
For research that involves approved drugs or devices, describe the FDA approved uses of this drug/device in relation to your protocol.
	
Congestive heart failure currently affects an estimated 6.6 million adults in the United States and ADHF accounts for ~ 1 million hospitalizations yearly¹. The main focus in the management of ADHF is on therapies directly responsible for removal of excess sodium and water. The most widely used therapy at present is higher than usual dose of oral or intravenous loop diuretics including furosemide, torsemide and bumetanide alone or in combination with thiazide like diuretics including chlorthalidone, hydrochlorthiazide or metolazone. However, resistance to the natriuretic effect and declining kidney function during diuresis are common occurrences. The mechanisms behind these relationships are complex and patient specific. The heart failure patients have severe underlying secondary hyperreninemic and hyperaldosteronism state due to reduced effective arterial blood volume (EABV) as a result of decreased cardiac output². Long-term loop diuretic use causes further RAAS activation by inhibiting sodium chloride transport at the macula densa and relative volume depletion as a result of failure to transfer the fluid from interstitium to vascular compartment at an acceptable rate. In addition, chronic use of loop diuretics causes enhanced sodium chloride co-transporter expression at distal collecting tubules leading to increased sodium absorption at this site resulting in resistance to natriuretic effect³. Addition of thiazide like diuretics overcomes the later problem; however, relative volume depletion causing further RAAS activation and excessive proximal tubular and collecting duct sodium absorption remains an issue.
 
Recently many other strategies including extracorporeal ultrafiltration and human recombinant low dose B-type natriuretic peptide – nesiritide have been used for removal of excessive fluid in addition to or in place of diuretics^{4,5}. However, none of these therapies have shown to be more beneficial than loop diuretics. In addition, blood based extracorporeal ultrafiltration requires use of invasive device and anti-coagulation. The possible explanation for failure to achieve the better outcomes with the above strategies is similar to the use of loop diuretic, i.e. further stimulation of neurohumoral system and RAAS by either rapid fluid removal or vasodilating property, respectively.

Item 4 Purpose and rationale 
Insert purpose, objectives and research questions/hypotheses here.
 
If you cut and paste from another document, make sure the excerpted material answers the question
	
Patients with CHF and cirrhosis share the same pathophysiology of arterial underfilling due to either decreased cardiac output or splanchnic vasodilatation respectively, resulting in stimulation of the sympathetic nervous system (SNS) and RAAS³. Subsequent hyperaldosteronism causes sodium retention and contributes to volume accumulation in both cirrhosis and HF. High-doses of aldosterone antagonists (spironolactone up to 400 mg/day) is a standard therapy to achieve negative sodium balance in cirrhotic patients⁶. However, in HF a low-dose aldosterone antagonist (spironolactone 25 mg/day) is recommended since it was shown to decrease mortality through anti-fibrosis action. Of note, this low dose of spironolactone does not have natriuretic effect⁷. Given that severe neurohormonal activation and hyperaldosteronism as a result of heart failure and further enhanced by loop diuretic is the pathophysiological basis of sodium retention and loop diuretic resistance in patients with ADHF similar to cirrhotic patients, neutralizing the effects of aldosterone with natriuretic doses of aldosterone antagonists may be a potential option to treat these patients⁸. In this regard, in a small trial of 6 avidly sodium retaining patients with heart failure, spironolactone 200 mg BID caused a marked increase in sodium excretion and indeed led to sodium balance over a few days with a clinically negligible rise in serum potassium concentration⁹. In another study, 81% of the patients with severe heart failure, who were resistant to high-dose loop diuretics (10 mg of bumetanide) and captopril, responded with increased natriuresis with the use of 100 mg/day spironolactone¹⁰.

	
However, main issue with the use of spironolactone, especially along with the use of angiotensin converting enzyme inhibitors (ACEi) or angiotensin receptor blockers (ARB), is the development of hyperkalemia. If used in conjunction with adequate doses of loop diuretics, the renal potassium retaining properties of aldosterone antagonists is counterbalanced by potassium-losing effect of loop diuretics by increasing the distal sodium delivery. Nonetheless, hyperkalemia is the most common reason for withdrawal for aldosterone antagonists. Patiromer, a nonabsorbed potassium binder, is a new FDA approved agent and has been shown to normalize serum potassium in patients with CKD and hyperkalemia on RAAS inhibitor in both outpatient as well inpatient setting. When given to hospitalized CKD patients with sustained moderate to severe hyperkalemia receiving at least one RAAS inhibitor while consuming a 60 mEq/day potassium diet in the controlled environment, single dose of patiromer caused a significant reduction in mean serum potassium by 7 hour. Mean serum potassium continued to decrease and after a second dose of patiromer fell to <5.5 mEq/l by 20 h. By 24 h, more than 80% of patients had a serum potassium <5.5 mEq/l. At 48 h, after four doses of patiromer, mean serum potassium had fallen by 0.75mEq/l, and more than 90% of patients had serum potassium values <5.5mEq/l. Over the entire study, mean serum potassium did not increase before the next dose of patiromer¹⁵.

--	--

Item 5
 
Study Population(s) Being Recruited
 
In your recruitment plan, how many different populations of prospective subjects do you plan to target? Provide number:
 
e.g., a population can be individuals with type 2 diabetes controlled with diet and/or a population of healthy controls. Or a population can be individuals attending an education program, etc.
 
List each different population on a separate row and provide a short descriptive label: (e.g., normal-healthy, diabetics, parents, children, etc.)
 
To add rows use copy & paste
	
Identify the criteria for inclusion:
	
Identify the criteria for exclusion:


Insert response here
	
 1. Patients \geq 18 years old 2. Hospitalized with history of chronic heart failure and at least one symptom (dyspnea, orthopnea or edema) and one sign (rales, peripheral edema, ascites, or radiographic pulmonary edema or pleural effusion) 3. Women of child bearing age with negative urine pregnancy test 	
 1. Acute coronary syndrome 2. Patients with a baseline eGFR < 30 ml/min by MDRD equation 3. Baseline potassium concentration \geq 5.5 mEq/L 4. Requirement for intravenous vasodilators or inotropic agents 5. Systemic infection 6. Patients with concomitant end-stage liver disease 7. Hemodynamically significant uncorrected valvular disease

		
 8. Patients with pulmonary embolism 9. Patients with high output heart failure 10. Pregnant patients
Insert response here	Insert response here	Insert response here

Item 6

Research Plan / Description of the Research Methods *a. Provide a comprehensive narrative describing the research methods. Provide the plan for data analysis (include as applicable the sample size calculation).*

Step-by-Step Methods:

Pre-screening: Patients meeting the inclusion and exclusion criteria will be approached to participate in the study. Informed consent will be taken at this time. These patients will receive intravenous loop diuretic per the discretion of treating physician and will be closely followed for weight loss and symptoms relief.

Screening: The patients who don't respond as measured by symptoms relief or <0.5 kg weight loss/day

- a) Despite furosemide \geq 160 mg IV total daily dose or equivalent dose of torsemide or bumetanide. (1 mg bumetanide = 10 mg torsemide = 20 mg furosemide). OR
- b) After 48 hours irrespective of diuretic dose.

will be considered for the study intervention. Patients who have not participated in the pre-screening phase and do not respond adequately to furosemide >160 mg iv daily dose will directly be enrolled into active intervention part of the study.

Intervention (High-Dose Spironolactone + Patiromer): Patients will be initiated on spironolactone 100 mg orally once daily along with patiromer 8.4 gm orally (if serum K >4.3 meq/L). The dose of loop diuretic will stay same during rest of the study period. On day 2, the dose of spironolactone will be titrated to 200 mg orally once a day depending on the diuretic response and lab results. Serum potassium and magnesium will be monitored twice a day. An EKG will be performed any time electrolytes are out of range. The dose of patiromer will be increased to 16.8 gm in patients with potassium levels exceeding 5.5 meq/L; or it will be held for serum K <4.3 mEq/L. Treatment will continue till patients achieve euvoolemia or get discharged. Euvoolemia is defined as resolution of symptoms and signs of volume overload.

Patients will be followed till achievement of euvoolemia or discharge. Daily assessment will be done for symptoms, and signs of volume overload including shortness of breath, orthopnea, paroxysmal nocturnal dyspnea, abdominal bloating, lower extremity edema, JVD, and body weight changes. Serum chemistry will be assessed twice a day and urine electrolytes once a day. Neurohormonal analysis will be done at the pre-screening, and at the end of the study duration.

Primary Safety measures:

- 1) Incidence of hyperkalemia as defined by serum K >5.5 meq/day.
- 2) Incidence of hypokalemia as defined by serum <3.5 meq/day
- 3) Renal function: assessed by daily serum creatinine

Primary Efficacy measures:

- 1) Weight loss: using same calibrated scale every day in hospital gown.
- 2) Symptom relief: assessed using a 5-point Likert scale describing magnitude of shortness of breath while the patient is in the supine position.

Secondary Efficacy measures:

	
 1) Urine sodium excretion: assessed by FENa% 2) Urine Sodium/Potassium ratio as a biomarker of aldosterone activity
	
Data Analysis Plan: This is a pilot exploratory study to assess safety and efficacy of high dose spironolactone with patiromer to find the sample size for large randomized study. A previous study utilizing combination of loop diuretics and high dose spironolactone had generated mean weight loss of 4.49 ± 1.51 kg compared to 0.57 ± 1.14 kg¹⁶. Given that this weight loss seems inflated, a mean weight loss of 2 ± 1.3 kg with two-sided t-testing, and a significance level of 5%, provides a power of 90% with 20 subjects [PASS Version 08.0.8, NCSS, Kaysville Utah 2008]. Assuming that loop diuretics resistance will be seen in 50% of the patients and there will be some lost to FU during active intervention period, we propose to pre-screen at least 300 subjects to enroll 60 subjects with the goal to have at least 20-30 completers in active intervention arm.

Item 7 Risks Section: Complete the following table to describe the risks of all research procedures listed in Step 2, Institutional Form (items 28-34). Do not list risks of Routine care procedures here.	
 N/A, Risks are described in the informed consent document – do not complete this table.	
Research procedures example: 
 • History and physical • Questionnaire • Laboratory tests Add or delete rows as needed	Risks List the reasonably expected risks under the following categories as appropriate:
Insert procedure here	Serious and likely;  Insert risk here or enter "none" Serious and less likely;  Insert risk here or enter "none" Serious and rare;  Insert risk here or enter "none" Not serious and likely;  Insert risk here or enter "none" Not serious and less likely  Insert risk here or enter "none"
Insert procedure here	Serious and likely;  Insert risk here or enter "none" Serious and less likely;  Insert risk here or enter "none" Serious and rare;  Insert risk here or enter "none" Not serious and likely;  Insert risk here or enter "none" Not serious and less likely  Insert risk here or enter "none"
Insert procedure here	Serious and likely;  Insert risk here or enter "none" Serious and less likely;  Insert risk here or enter "none" Serious and rare;  Insert risk here or enter "none" Not serious and likely;  Insert risk here or enter "none" Not serious and less likely  Insert risk here or enter "none"

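### Weight loss in this single arm mixes continuing loop-diuretic loss with any spironolactone effect, and the stated 90% power is that of a two-group test

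*Combined protocol and SAP*

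**What the plan says.** The Research Design/Plan describes a "prospective exploratory single-arm, open-label pilot study". Four sets of rules bear on its weight outcome.

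- **Entry** (Screening, in the summary and in Item 6): patients are considered for the intervention if they do not "respond as measured by symptoms relief or <0.5 kg weight loss/day", either despite a stated loop-diuretic dose or after 48 hours at any dose. Slow continuing loss is compatible with entry, and so are stable weight and weight gain.
- **Background treatment** (Intervention): "The dose of loop diuretic will stay same during rest of the study period".
- **Judging the result** (Treatment Failures; Item 6, Primary Efficacy measures): "Patients will be considered high dose spironolactone failure if they do not achieve a net negative body weight after a minimum of 5 days". Weight loss on a calibrated scale is a primary efficacy measure. Nothing is subtracted from it, and no reference value other than zero appears.
- **Sizing** (Item 6, Data Analysis Plan): the pilot is "to find the sample size for large randomized study". An earlier study is cited with a "mean weight loss of 4.49 ± 1.51 kg compared to 0.57 ± 1.14 kg". Calling that loss inflated, the plan takes "a mean weight loss of 2 ± 1.3 kg with two-sided t-testing" at the 5% level and says this "provides a power of 90% with 20 subjects".

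Pre-screening follows weight on the loop diuretic, but no listed measure uses those weights. Some patients may enter the intervention without pre-screening.

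**The concern.** A patient losing 0.4 kg/day at entry who simply continues on the unchanged loop dose loses 0.4 × 5 = 2.0 kg in 5 days. That patient is not a failure under the net-weight rule and supplies exactly the assumed 2 kg, with no contribution from spironolactone.

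A randomized trial of adding spironolactone would estimate the loss on both drugs minus the loss on loop diuretic alone. The pilot's single arm measures only the first term. If that total were entered as the group difference, the next trial would be sized on the wrong quantity.

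The power statement raises a related question. If 2 kg is a group difference, one arm cannot estimate it. If it is one arm's change, the quoted power should follow from a one-sample test.

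**Working it through.** **Inputs.** Mean 2 kg, SD 1.3 kg, two-sided 5%, 90% power, 20 subjects, and comparator loss 0.57 kg are from the Data Analysis Plan. The entry ceiling of 0.5 kg/day is from Screening. The 5 days come from Treatment Failures. The mean entry rate, *b*, is not in the documents and is varied. All power figures use the noncentral t distribution.

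**1. Reproducing the plan's figure.**

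- Two groups of *n*: noncentrality = 2 / (1.3 × √(2/*n*)). With *n* = 10 this is 2 / 0.581 = 3.44 on 18 df, and power is **0.902**. With 9 per group it is 0.865; with 20 per group, 0.997.
- One arm of 20 against zero: noncentrality = 2 / (1.3/√20) = 2 / 0.291 = 6.88 on 19 df, and power is above **0.999**. Seven patients would already give 0.920.
- One arm of 20 against 0.57 kg, reading 2 kg as the arm's total: (2 − 0.57) / 0.291 = 4.92, and power is **0.997**.

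Of these, only two groups of 10 match 90% with 20 subjects.

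**2. What one arm of 20 offers.** With SD 1.3 it has 90% power for a mean change of about 1.0 kg from its reference. The 95% interval is ± 2.093 × 0.291 = ± 0.61 kg.

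**3. Effect on the next trial (illustration).** Write total loss = continuing loop-diuretic loss + added effect. Suppose the pilot observes 2 ± 1.3 kg and the entry rate continues unchanged for 5 days. The added effect is then 2 − 5*b*.

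| *b* (kg/day) | Added effect (kg) | Per arm for 90% power | Power with 10 per arm |
|---|---|---|---|
| −0.1 (gaining) | 2.5 | 7 | 0.98 |
| 0 | 2.0 | 10 | 0.90 |
| 0.1 | 1.5 | 17 | 0.68 |
| 0.2 | 1.0 | 37 | 0.37 |
| 0.3 | 0.5 | 144 | 0.13 |
| 0.4 | 0 | none | – |

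Duration matters too. At 0.2 kg/day, 3 days gives an added effect of 1.4 kg and 20 per arm; 7 days gives 0.6 kg and 100 per arm.

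**4. What zero as reference allows.** Suppose spironolactone adds nothing and individual 5-day loss is Normal with mean 5*b* and SD 1.3. The share with net loss is Φ(5*b*/1.3): 50%, 65%, 78%, 88% and 94% for *b* = 0, 0.1, 0.2, 0.3 and 0.4. A test of 20 patients against zero would be significant with probability 0.37 at 0.1 kg/day and 0.90 at 0.2. Against 0.57 kg these fall to 0.06 and 0.29.

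**5. Would subtracting each patient's entry rate cure this?** Not alone. Entry selects on the same noisy rate that would be subtracted. A no-effect simulation assumed a mean rate of 0.3–0.5 kg/day, between-patient SD 0.3–0.5 and weighing error SD 0.3–0.7 kg. The within-patient change showed a false 5-day benefit of about 0.9 to a little over 4 kg with a one-day entry window, usually worse than uncorrected total loss. With a two-day window the false benefit was about 0.3–2.0 kg, and the comparison with total loss was mixed.

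**The case against.** The strongest reply has four parts.

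- **The plan never says that total loss will be carried forward.** This stands. A reader might infer it, since weight loss is the only weight-based efficacy measure and sizing is the declared purpose. But the text does not say whether the mean, the SD or the retention rate will be used. What can be said is that the estimate is unspecified.
- **The 2 kg may already be net of a comparator.** This also stands. A reader might subtract 0.57 from 2 to get 1.43 kg, which would need 19 per arm, and treat that as the plan's own figure. The documents do not support it. The 90% reproduces only with 2 kg as a group difference. Half the cited difference, (4.49 − 0.57)/2 = 1.96, and the pooled SD, √((1.51² + 1.14²)/2) = 1.34, lie close to 2 ± 1.3. On that reading the subtraction counts the comparator twice. The plan also gives no duration or comparator treatment for the 0.57 kg.
- **The background rate is unknown.** True: 0.5 kg/day is a ceiling, and the target population is resistant to loop diuretics. Neither the direction nor the size of the error is established.
- **An exploratory single-arm pilot is not expected to isolate an effect.** Fair, and no control arm is asked for here. But this pilot is declared to serve sample-size planning, so its plan should say which quantity it can supply.

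The failure rule should not be over-read either. The same section also treats non-responders as failures and includes them in the primary analysis, and no analysis of the failure count is listed.

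**Conclusion.** The concern holds in a limited form. The entry rule, the fixed loop dose and the zero reference mean that total weight loss in this arm cannot be read as spironolactone's added effect. Used alone as the next trial's group difference, it would overstate that effect if patients were losing weight at entry and understate it if they were gaining. It would be unbiased on this account if loop-only change averaged zero.

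A reader might conclude that the next trial will be too small. The documents do not show that, because they give neither the estimate to be used nor the mean entry rate. The span from 7 per arm to no finite number rests on an assumed constant rate for 5 days, an observed 2 kg and SD 1.3.

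The power finding needs none of the entry-rate assumptions: 90% with 20 subjects matches two groups of 10, and is not the power of one arm of 20. That arm is not too small for a 2 kg change from zero; the statement describes a different design. Both matters should be corrected.

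**What to change.** Four changes, mostly a few sentences in the Data Analysis Plan:

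1. Restate the 20-subject power or precision for one arm and name the reference value. With SD 1.3, the precision is about ± 0.61 kg.
2. State that total loss in this arm will not be used alone as the next trial's between-group effect. Use the pilot for the SD and retention, and size the next trial over a range of assumed loop-only losses, with 0.57 kg as one scenario.
3. Report each patient's change in kg/day from the entry window to treatment, with a 95% interval, in all patients who take a dose, and label it descriptive. Entry weights would come from pre-screening or the chart.
4. Reconcile the entry and failure wording, including how symptoms and weight combine at entry. No threshold or clinical rule is proposed here.

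The cost is small, since weights are already followed in pre-screening and taken daily on treatment. There are limits. The within-patient change is biased upward by regression to the mean, most with a one-day window. Loop doses in pre-screening are at the physician's discretion and may differ from the dose later held fixed. Some directly enrolled patients may have no entry weights. The next trial may also prove larger than total loss alone would suggest.

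### Follow-up ends at the same event as treatment, so for patients treated to euvolemia or discharge the primary safety measures count no potassium or creatinine change after the last spironolactone dose

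*Combined protocol and SAP*

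**What the plan says.** The Primary Aims put safety first: "Evaluate the safety of high-dose spironolactone in combination of Patiromer in acute decompensated heart failure patients". Item 6 lists three primary safety measures: "Incidence of hyperkalemia as defined by serum K >5.5 meq/day", "Incidence of hypokalemia as defined by serum <3.5 meq/day" (units as printed), and renal function from daily serum creatinine. None of the three carries a time window.

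Two sentences in Item 6 set the period of observation. For treatment: "Treatment will continue till patients achieve euvoolemia or get discharged". For follow-up: "Patients will be followed till achievement of euvoolemia or discharge". Serum chemistry is scheduled twice a day within that period, and the last listed assessment is a neurohormonal sample at the end of the study. The research plan describes no visit, laboratory check or adverse-event window after that.

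The Treatment Failures paragraph of the opening summary adds that the treating physician may stop high-dose spironolactone at any time.

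**The concern.** When treatment and observation close together, the effect of the last dose or doses is seen only as far as it appears before the closing event. The plan's rationale (Item 4) names hyperkalemia as the main problem with spironolactone and the most common reason for withdrawing the drug class, so this is the outcome for which a safety reader would most want the end of exposure covered.

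Two kinds of patient are affected. One becomes euvolemic but stays in hospital: on the plain reading (whichever event comes first) follow-up closes, and a potassium above 5.5 the next morning is not counted even if routine care measures it. The other is discharged at the end of treatment: no later value is called for at all.

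At stake is what the first primary aim can claim. The Data Analysis Plan says the pilot is to assess safety and efficacy in preparation for a large randomized study. An incidence that stops at the last dose could be carried forward as if it covered the full consequence of exposure.

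**Working it through.** The plan has no figure to reproduce here. Its only calculation, 90% power with 20 subjects, is for weight loss and has no bearing on the safety window.

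**Step 1. The sentences side by side**

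| Item | Ends at | Place |
|---|---|---|
| Study treatment | Euvolemia or discharge | Item 6, Intervention; also the opening summary |
| Follow-up | Euvolemia or discharge | Item 6, Intervention |
| Primary safety measures | Not stated | Item 6, Primary Safety measures |

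Because the safety measures have no window of their own, the follow-up sentence sets it. For a patient treated to the closing event, time counted after the end of treatment is zero.

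**Step 2. The exception.** A patient whose spironolactone is stopped early is, on the text, still followed until euvolemia or discharge with twice-daily chemistry. Some values after the last dose are then counted. The gap therefore concerns patients treated to the closing event.

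**Step 3. Direction.** Let a be the proportion with a counted potassium event, and b the proportion of the remainder whose first event comes after follow-up closes.

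- Counted incidence: a
- Incidence over exposure plus after-effect: 1 − (1 − a)(1 − b) = a + (1 − a)b
- Difference: (1 − a)b, which is zero or positive and never negative

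This holds for hyperkalemia and hypokalemia, which have limits. The plan sets no event limit for creatinine, so the inequality applies to it only once one is set. As a daily series, creatinine is simply cut off.

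**Step 4. Weight of one patient.** The Data Analysis Plan aims for at least 20 to 30 completers. With completers as denominator, one uncounted patient is 1/20 = 5.0 or 1/30 = 3.3 percentage points.

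**Step 5. Illustration under assumed rates.** The documents give neither a nor b. Take a = 5%, vary b, and suppose all n completers are treated to the closing event. Expected uncounted patients = n(1 − a)b. The chance of missing at least one = 1 − [1 − (1 − a)b]^n.

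| n | b | Expected counted | Expected uncounted | Chance of missing at least one |
|---|---|---|---|---|
| 20 | 2% | 1.0 | 0.38 | 32% |
| 20 | 5% | 1.0 | 0.95 | 62% |
| 20 | 10% | 1.0 | 1.90 | 86% |
| 30 | 2% | 1.5 | 0.57 | 44% |
| 30 | 5% | 1.5 | 1.43 | 77% |
| 30 | 10% | 1.5 | 2.85 | 95% |

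If b is zero, nothing is missed. The table shows how sensitive a sample of this size is to the rule. It is not an estimate of the loss.

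**The case against.** The best defence is that on-treatment, in-hospital incidence is a legitimate safety quantity, and the plan nowhere claims safety after discharge. In an exploratory single-arm pilot that may be all that is intended. This stands to the extent that a conclusion confined to the observed period would not be wrong. But the aim is worded without that limit, and nothing in the plan supplies it.

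Several stronger readings are tempting, and the documents do not support them:

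- A reader might infer that no value after a last dose is ever counted. Early stopping contradicts this, and those patients may include some stopped for potassium or creatinine.
- A reader might take the patiromer result, "At 48 h, after four doses of patiromer, mean serum potassium had fallen by 0.75mEq/l", as evidence of late harm. It describes potassium falling during repeated dosing in CKD patients with hyperkalemia. The other time reference in Item 4, a response to spironolactone over a few days, concerns sodium balance during dosing in 6 patients, and the same sentence reports a clinically negligible potassium rise. Neither describes what follows the last dose.
- A reader might assume 48 h of continuing risk and compute an uncounted share of 2/(d + 2) for d treatment days: 50% at d = 2, 33% at d = 4, 22% at d = 7. No document supports 48 h. The result is a share of time, and it equals a share of events only if the event rate is the same after the drug stops as during dosing. Two days is also an extreme case: entry requires poor response to loop diuretics, and the day 2 titration depends on diuretic response and laboratory results.
- A reader might infer that patients go unmonitored. The end of protocol follow-up does not mean that routine inpatient tests stop.

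The consent document, to which Item 7 refers for risks, was not available for this review and could mention a later contact. A value that counts toward a primary safety measure should still be defined in the research plan.

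**Conclusion.** The concern holds for patients treated to euvolemia or discharge. It is a stated rule that limits the first primary aim, not merely a missing detail, and it does not invalidate the study. The conclusion rests on the plain reading of the follow-up sentence and on the absence of any later safety check in the research plan. If that sentence were instead read as the later of the two events, values up to discharge would count and the gap would begin at discharge.

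The direction is certain for any first event after follow-up closes, because it can only be missed. The size is unknown. The documents allow no estimate of missed events, and the assumed rates above should not be quoted as one.

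**What to change.** Change the follow-up sentence in Item 6 so that potassium and creatinine safety data are counted until hospital discharge and do not stop at euvolemia, using results already drawn in routine inpatient care. Add any available result within a post-dose window whose length the sponsor sets; the documents give no basis for choosing it here. State this window beside the three primary safety measures. Report events on treatment and events after the last dose separately. Where no value after discharge is obtained, limit the safety conclusion to the observed in-hospital period.

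Counting to discharge adds nothing for a patient whose treatment runs up to discharge. For that patient only the sponsor's window or the limited conclusion helps.

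The cost is a short amendment and slightly more data collection. The reported event rate may rise slightly. No dose or treatment rule changes.
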